Study Objectives	To assess the efficacy and safety of two dose regimens of mebendazole: i) 100 mg solid tablets twice a day for 3 days, and ii) one dose of 500 mg solid tablets of mebendazole in participants aged 6-12, inclusive, infected with hookworm. The primary objective of the trial is to assess the cure rate (CR) of a 3-day regimen of mebendazole against hookworm and a single dose mebendazole treatment. The secondary objectives are to determine if the multi-dose regimen is superior to the single dose regimen, evaluate the efficacy against concomitant soil-transmitted helminth infections, and assess the safety of both mebendazole regimens.
Study -design	Double blind, randomized trial (both participants and outcome assessors are blinded)
Study product intervention	Mebendazole
Comparator(s)	None
Key inclusion / Exclusion criteria	Inclusion: individuals aged between 6 and 12 with a hookworm infection, absence of major systemic illnesses, written informed consent signed by parents/caregivers; and oral assent by the participants. Exclusion: Menarche, any abnormal medical conditions or chronic disease, negative diagnostic result for hookworm, no written informed consent

Primary Endpoints	CR against hookworm
Secondary Endpoints	Egg reduction rate (ERR, based on geometric means) against hookworm, CR/ERR against A. lumbricoides and T. trichiura , safety
Exploratory Endpoints	
 • Sensitivity of Kato Katz compared to quantitative polymerase chain reaction assays • Prevalence of mebendazole genetic resistance markers • Prevalence of STH species
Interim Analyses	None
Study Duration	12 weeks total; up to 8 weeks per participant
Schedule	07/2017 of first-participant in (planned) 10/2017 of last-participant out (planned)

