Measurements & procedures	
Two stool samples will be collected if possible on two consecutive days or otherwise within a maximum of 5 days apart. The medical history of the participating individuals will be assessed with a standardized questionnaire, in addition to a clinical examination carried out by the study physician on the treatment day.
 
Randomization of participants into the two treatment arms will be stratified according to intensity of infection. Participants will be interviewed before treatment for clinical symptoms and 3 hours after every morning treatment and 24 hours after every morning treatment about the occurrence of adverse events. The efficacy of the treatment will be determined 14-21 days post-treatment by collecting another two stool samples. All stool samples will be examined with duplicated Kato-Katz thick smears.

Statistical Analyses	
The primary analysis will include all participants with primary end point data (available case analysis). Supplementary, two sensitivity analyses will be conducted imputing all missing endpoint data as treatment failures or all as treatment success. CRs will be calculated as the percentage of egg-positive participants at baseline who become egg-negative after treatment. CRs will be compared by using unadjusted logistic regression. To assess model robustness with respect to covariates, adjusted logistic regressions (adjustment for age, sex, school, weight and strata) will be performed.
 
Geometric and arithmetic mean egg counts will be calculated for the different treatment arms before and after treatment to assess the corresponding ERRs. Bootstrap resampling method with 5,000 replicates will be used to calculate 95% confidence intervals (CIs) for ERRs and the difference of the ERRs.

GCP statement	This study will be conducted in compliance with the protocol, the current version of the Declaration of Helsinki, ICH-GCP E6 as well as all national legal and regulatory requirements.
Key explanation for the inclusion of	This study will be carried out in individuals aged 6-12 years old, since an infection with hookworm and other soil-transmitted

participants	helminths occurs most often in this age group.
Recruitment procedure	The study will be carried out in primary schools in Pemba Island, Tanzania.
Coverage of damages	Winterthur Police Nr. 4746321, National Insurance Cooperation of Tanzania LTD, GTA No: 00062.

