4.5. Schedule of visits

Table 2 briefly presents the distribution of tasks along the trial. Further detail is available in Appendix 2.

Table 2. Schedule of visits during treatment period.

Screening							Follow-up
- 21 to -1	-3 to -1	D1	D2	D3	D4	D5	14 to 21 days
		Hours					

	days	days	0	3	10	0	3	10	0	3	10	0	0	
Diagnosis (stool examination)	X													X
Informed consent	X													
Demographics	X													
Medical History		X												
Administration of treatment/placebo			X		X	X		X	X		X			
Physical Examination, including menarche and anemia assessments		X												
Capturing AEs/ SAE				X		X	X		X	X		X	X	
Administration of albendazole (still infected at follow-up)														X

5. Selection of the trial subjects

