6.1. Adverse event definitions

The term “adverse event” could include any of the following events which develop or increase in severity during the course of the study, after administration of the study product:

- a) Any unfavourable and unintended signs, symptoms or disease temporally associated with the use of a medicinal product, whether or not considered related to the condition under study and the study product;
- b) Any abnormality detected during physical examination.

The medical conditions present at the initial trial visit that do not worsen in severity or frequency during the trial will not be defined as adverse events but as be considered baseline medical conditions. For the purpose of this trial, disease progression and relapse will be considered as treatment failure, not as an Adverse Event.

The observation time for adverse events starts when the treatment is initiated until day 5 (48 hours after last drug administration).

These data will be recorded on the appropriate CRF sections, regardless of whether they are thought to be associated with the study or the drug under investigation. Associated with the use of the drug means that there is a reasonable possibility that the event may have been caused by the drug (see also relatedness definitions below).

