6.2. Methods of recording and assessing adverse events

Patients will be kept for observation for at least 3 hours following each morning treatment for any acute adverse events. During the reporting period, any unfavorable changes in the subject’s condition will be recorded as adverse events, whether reported by the subject or observed by the Investigator. In case of any abnormal finding, the local study physician will

perform a full clinical examination and findings will be recorded. An emergency kit will be available on site to treat any medical conditions that warrant urgent medical intervention.

In addition, patients will be also interviewed by a nurse and/or a physician about the occurrence of adverse events 24 hours after every morning treatment (before the next treatment) and 48 hours after the last treatment (day 5) (Table 2).

Information on all adverse events (onset, duration, intensity, seriousness and causality) will be immediately entered in the appropriate adverse event module of the case report form (CRF) which is considered as a source document. For all adverse events, sufficient information will be pursued and/or obtained so as to permit i) an adequate determination of the seriousness of the event (i.e. whether the event should be classified as a serious adverse event); ii) an assessment of the casual relationship between the adverse event and the study treatments (i.e. whether the event should be classified as an adverse drug reaction); and iii) an assessment of intensity of adverse events by the study physician.

All serious adverse events, unexpected adverse drug reactions, or SUSARs must be reported as described in Section 6.3.

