7.3. Description of statistical methods

The primary available case analysis will include all participants with primary end point data. In addition, an intention-to-treat analysis will be conducted considering all participants with missing endpoint data as treatment failure or all as treatment success to ensure that the results are not sensitive to potential loss to follow-up bias. CRs will be calculated as the percentage of egg-positive children at baseline who become egg-negative after treatment. EPG will be assessed by adding up the egg counts from the quadruplicate Kato-Katz thick smears and multiplying this number by a factor of six. The ERR will be calculated as:

$$ERR = 1 - \frac{\frac{1}{n} e^{\sum \log(EPG_{follow-up} + 1)} - 1}{\frac{1}{n} e^{\sum \log(EPG_{baseline} + 1)} - 1}$$

In the primary model we estimate the difference among CRs by using unadjusted logistic regressions. In a subsequent analysis an adjusted logistic regression (adjustment for age, sex, school, weight and strata) will be performed.

Geometric mean egg counts will be calculated for the different treatment arms before and after treatment to assess the corresponding ERRs. Bootstrap resampling method with 5,000 replicates will be used to calculate 95% confidence intervals (CIs) for ERRs and the difference between the ERRs.

Adverse events will be evaluated descriptively as the difference of proportion reporting adverse events before and after treatment.

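### The only planned adverse event analysis is a before-versus-after difference that conflicts with the protocol's own definition, and no summary by randomised arm is specified

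*Combined protocol and SAP*

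**What the plan says.** Section 7.3 states: "Adverse events will be evaluated descriptively as the difference of proportion reporting adverse events before and after treatment". It names no arm, time point or interval. The statistical part of the synopsis contains no AE analysis, so this sentence is the whole plan.

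The synopsis lists among the secondary objectives to "assess the safety of both mebendazole regimens", and section 3 makes safety a secondary endpoint.

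Section 6.1 restricts AEs to events "which develop or increase in severity during the course of the study, after administration of the study product". It sets the window as follows: "The observation time for adverse events starts when the treatment is initiated until day 5 (48 hours after last drug administration". It also excludes unchanged pre-existing problems: "The medical conditions present at the initial trial visit that do not worsen in severity or frequency during the trial will not be defined as" AEs.

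The Table 2 row "Capturing AEs/ SAE" has seven crosses: day 1 at 3 h, day 2 at 0 h and 3 h, day 3 at 0 h and 3 h, day 4 and day 5. None comes before the first dose. The synopsis (Measurements & procedures) adds a pre-dose enquiry that has no row in Table 2: "Participants will be interviewed before treatment for clinical symptoms".

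**The concern.** The statistic needs a proportion of children with AEs before treatment, and section 6.1 leaves no such quantity. An analyst must either enter zero or substitute the baseline symptom interview. The second choice may set one enquiry against seven, so that the number of times a child is asked becomes mixed up with the effect of the drug.

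The randomised comparison is also left unused. Both arms have the same six dosing times with matching placebo (Table 3) and the same AE interviews, so in expectation background symptoms and interview count are equal between arms. For egg counts, section 7.3 asks for results by arm and a confidence interval for the difference in egg reduction rates. For AEs it asks for neither. Section 2 describes the trial as, to the authors' knowledge, the first randomised comparison of these two regimens, so its AE table is likely to be read as a comparison of them.

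**Working it through.** The plan states no figure for safety, so there is none to reproduce. The documents give no AE rate or background symptom rate; the rates and correlations below are assumptions.

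**Inputs from the documents**
- Enquiries before the first dose: one symptom interview (synopsis).
- AE captures after the first dose: 7 (Table 2). Section 6.2 agrees: three observation periods after the morning doses, three 24-hour interviews and one on day 5.
- Participants per arm: 90 (section 5.5).

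**Reading 1: the section 6.1 definition governs.** The proportion before treatment is 0, so the difference is (post-dose proportion) − 0 = post-dose proportion. If the arms are pooled, it cannot separate the regimens. AE proportions of 10% and 30% give (10 + 30)/2 = 20 points, and 20% in each arm gives (20 + 20)/2 = 20 points.

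**Reading 2: one baseline symptom interview against any report over seven captures, with no drug effect.** Let p be the chance of a report at each interview and ρ the within-child correlation.
- Independent reports: P(any) = 1 − (1 − p)^7. At p = 0.05 this is 1 − 0.95^7 = 0.302.
- Correlated reports (beta-binomial): a = p(1 − ρ)/ρ, b = (1 − p)(1 − ρ)/ρ, and P(any) = 1 − ∏ (b + i)/(a + b + i) for i = 0 to 6. At p = 0.05 and ρ = 0.3, a = 0.117 and b = 2.217, which gives 0.169. At ρ = 0.6, a = 0.033 and b = 0.633, which gives 0.105.
- Full correlation: P(any) = p, so there is no increase.

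| Before (one interview) | After, ρ = 0 | After, ρ = 0.3 | After, ρ = 0.6 | After, ρ = 1 |
|---|---|---|---|---|
| 2% | 13.2% | 7.1% | 4.3% | 2% |
| 5% | 30.2% | 16.9% | 10.5% | 5% |
| 10% | 52.2% | 31.4% | 20.2% | 10% |
| 20% | 79.0% | 54.1% | 37.4% | 20% |

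At 5% the spurious increase is 25.2, 11.9, 5.5 or 0 points.

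**Reading 3: baseline against one post-dose time point at a time.** Each side is a single enquiry with chance p, so the expected difference without a drug effect is p − p = 0.

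**Between-arm contrast.** With no difference between the regimens its expected value is 0, whatever the number of interviews. The 95% half-width with 90 per arm is 1.96 × √(2p(1 − p)/90). At p = 0.20 this is 1.96 × √(0.32/90) = 0.117. The same formula gives 6.4 points at 5%, 8.8 at 10%, 13.4 at 30% and 14.6 at 50%. For 10% against 30% the standard error is √(0.09/90 + 0.21/90) = 0.0577, and the difference is 20 points (95% CI 8.7 to 31.3).

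**The case against.** Several points against the concern have force.

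- **Arms.** A reader might infer that the plan cannot compare the regimens. The documents do not support that. Section 7.3 neither pools the arms nor forbids showing the change by arm, and the objective to assess the safety of both regimens can be met by describing each one. What stands is that no by-arm summary or contrast is specified.
- **Apparent increase.** A reader might also infer that the before-after statistic always shows a rise. It does so only under reading 2, and only if reports are not fully correlated. Section 7.3 does not say that the seven captures are collapsed into any report. The 25-point figure is the independence extreme of an assumed rate, and some interviews of the same child are 3 hours apart.
- **Existing safeguards.** Section 6.1 is already close to a treatment-emergent definition. Table 2 schedules medical history and physical examination on days −3 to −1, and section 6 includes baseline medical conditions in the safety assessment. This is true, but it makes a before-after difference in AEs harder to interpret, because baseline conditions are by definition not AEs. Serious adverse events are reported from consent (section 6.1.4), which gives no baseline for ordinary AEs.
- **Limits of the remedy.** Both arms receive mebendazole, so a contrast between them also cancels any drug effect that they share. This stands and should be stated in the plan.
- **Importance.** The analysis is descriptive and secondary, section 6 notes that few AEs have been reported with mebendazole, and the interval is wide. A descriptive analysis is acceptable at this size. That bears on how much can be concluded, and does not rescue the statistic.

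**Conclusion.** The point holds. The one planned AE statistic is either degenerate, because its first term is zero under section 6.1, or undefined until someone decides what counts as before and after. One plausible choice produces an increase without any drug effect: at an assumed 5% per interview, from 5.5 points (correlation 0.6) to 25 points (independence), falling to none under full correlation or with single time points. These sizes rest on assumed rates and correlations. The conflict with section 6.1 and the absence of any by-arm summary rest on the text alone.

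The defect should be corrected before the data are analysed. It does not touch the primary endpoint, the sample size or data collection.

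**What to change.** Replace the AE sentence in section 7.3 with the following.

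1. Report the number and proportion of participants with at least one treatment-emergent AE (new, or worse than at the pre-dose symptom interview), and with each common symptom, by randomised arm.
2. Give the between-arm risk difference with its 95% CI, presented descriptively and without a test.
3. Show baseline symptoms separately by arm, and use them only to decide whether an event is treatment-emergent.
4. State that both arms receive mebendazole, so the contrast measures relative safety, while the by-arm proportions describe each regimen's own profile.

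Add the pre-dose symptom interview, which is already planned in the synopsis, to Table 2.

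The cost is revised wording, one table entry and a small additional analysis. No new participants, visits or data are needed.

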7.4. Description of data management

The investigators are responsible for an adequate data quality. Prior to the initiation of the study, a short investigator's meeting will be held with the investigators and their study

coordinators and a member from Swiss TPH. This meeting will include a detailed discussion of the protocol, performance of study procedures (SOPs from previous studies available on site), CRF completion, and specimen collection and diagnostic methods.

Screened patients will be listed in a confidential “subject screening log”. Enrolled patients will be listed in a confidential “subject enrolment log” and attributed a unique study number; this document will constitute the only source to decode the pseudonymised data and will only be accessible to the local principal investigator. All data that have been hand-entered in the database will be verified by a double-key entry procedure in a validated electronic data base system and error, range and consistency checks will be programmed. Any discrepancies will be reviewed against the hard copy CRF and corrected. Electronic data files will be stored on secured network drives with restricted access for study personnel only. Data analysis will be conducted with pseudonymised data and reporting of findings will be fully anonymised.

Essential infrastructure such as lockable cabinets for safe storage of hardcopy data will be made available. Network drives with restricted access for authorised personnel only and appropriate analysis software are available.

8. Duties of the investigator

8.1. Investigator’s confirmation

This trial will be conducted in accordance with the protocol, International Conference on Harmonisation Good Clinical Practice E6 (R2) (ICH-GCP) and the current version of the Helsinki Declaration.

All protocol modifications must be documented in writing. A protocol amendment can be initiated by either the Sponsor/PI or any Investigator. The Investigator will provide the reasons for the proposed amendment in writing and will discuss with the Sponsor/PI and Co-PIs. Any protocol amendment must be approved and signed by the Sponsor/PI and must be submitted to the appropriate Independent Ethics Committee (IEC) for information and approval, in accordance with local requirements, and to regulatory agencies if required. Approval by IEC must be received before any changes can be implemented, except for changes necessary to eliminate an immediate hazard to trial subjects, or when the change involves only logistical or administrative aspects of the trial, e.g. change of telephone number(s).

8.2. Damage coverage

A general liability insurance of the Swiss TPH is in place (Winterthur Police Nr. 4746321) and a patient liability insurance will be issued by the National Insurance Cooperation of Tanzania LTD, which will cover any eventual study related injuries or deaths.

9.1. Independent Ethics Committee (IEC)

The study will be submitted for approval by the institutional research commission of the Swiss TPH and the ethics committees of Switzerland (EKNZ: Ethical Commission of northwest/central Switzerland) and Zanzibar (ZAMREC: Zanzibar Medical Research and Ethics Committee). The study will be undertaken in accordance with the Declaration of Helsinki and good clinical practice (GCP).

9.2. Evaluation of the risk-benefit ratio

Few adverse events have been reported for mebendazole (package insert Appendix 3). The most common reported adverse events are abdominal cramps, headache, diarrhoea, fever and fatigue [17, 23, 26].

All participants will benefit from a clinical examination and a treatment against STHs. All participants in whose stool we still find hookworm eggs will be treated with albendazole (according to WHO recommendations).

9.3. Subject information and consent

Community meetings will be conducted to explain to caregivers the purpose and procedures of the study. Parents or caregivers attending this meeting will receive a small provision to cover their costs for transportation (~US\$ 2). Their level of comprehension of the trial's purpose and procedures will then be assessed using a short multiple-choice questionnaire. Finally, one of the parents/caregiver of an eligible individual will be asked to sign a written informed consent form (translated into the local language, *i.e.* Kiswahili) after having had sufficient time for reflection of their child's participation. Even if the participant gives oral assent, the parent/caregiver has to sign the consent. In case the parent/caregiver is illiterate, an impartial witness that can read and write has to sign the consent and the parent/caregiver to give a thumb print. Participation is voluntary and individuals have the right to withdraw from the study at any given point in time with no further obligations. Participation itself will not be awarded with compensation. Only after the informed consent form is signed will participants undergo any screening procedures.

9.4. Subject Confidentiality

The obtained data will be handled strictly confidentially. Only members of the study team will have access to the data. Personal data will be coded for data analysis. The codes will be filled with the participant's identity on a separate file (subject identification list) and filled in a secured place at the Public Health Laboratory Ivo de Carneri and will only be accessible to investigators. No names will be published at any time, and published reports will not allow for identification of single subjects. Confidentiality and anonymity will be ensured throughout the entire research project.

The investigators have all been trained in GCP. None of the investigators declare to have any conflicts of interest.

9.5. Subjects requiring particular protection

This study will be carried out in children, since an infection with hookworm often occurs in this age group and they are at high risk of infection. Our trial will produce more evidence to support the search of safer and more effective treatment of STH infections in children.

10. Quality control and quality assurance

10.1. Monitoring and auditing

We will work with a locally based monitor. He/she will conduct site visits to the investigational facilities for the purpose of monitoring the study. Details will be described in a separate monitoring plan. The investigator will permit them access to study documentation and the clinical supplies dispensing and storage area. Monitoring observations and findings will be documented and communicated to appropriate study personnel and management. A corrective and preventative action plan will be requested and documented in response to any audit observations. No sponsor initiated audits are foreseen, but audits and inspections may be conducted by the local regulatory authorities or ethics committees. The Investigator agrees to allow inspectors from regulatory agencies to review records and is encouraged to assist the inspectors in their duties, if requested.

10.2. Access to data, handling of data and samples (data protection), archiving (place, duration) and destruction

Information about study subjects will be kept confidential and managed accordingly. A CRF will be completed for each subject enrolled into the clinical study. The investigators will review, and approve each completed CRF. The study CRF is the primary data collection instrument for the study. All data requested on the CRF must be recorded. All missing data must be explained. If a space on the CRF is left blank because the procedure was not done or the question was not asked “N/D” will be entered. If the item is not applicable to the individual case “N/A” will be written. All entries will be printed in blue ink. All corrections must be initialled and dated.

All data on parasitology and questionnaires about adverse events and self-reported clinical signs and symptoms will be doubled entered into a database by two independent persons and cross-checked. Discrepancies between data entries will be corrected by consulting the hard copy.

The collected data together with the hard copy CRFs, ICFs and other study documents will be stored at server of the Public Health Laboratory (PHL) in Pemba and are encrypted with Secure Sockets Layer (SSL).

The results of the research study will be published, but subjects' names or identities will not be revealed. Records will remain confidential. To maintain confidentiality, the Sponsor-Investigator will keep records in locked cabinets and the results of tests will be coded to prevent association with participant's names. Data entered into the ACCESS data entry mask will be accessible only by authorized personnel directly involved with the study and will

be encoded. Subject-specific information may be provided to other appropriate medical personnel only with the subject's permission.

After the study has been completed all samples will be destroyed and research data and related material will be kept for a minimum of 15 years to enable understanding of what was done, how and why, which allow the work to be assessed retrospectively and repeated if necessary.

10.3. Data entered directly in the Case Report Form (CRF) – definition of source data

Source Data are the clinical findings and observations, laboratory data maintained at the study site. Source data are contained in source documents. Local authorities are allowed to access the source data. Data will be entered directly onto the case report forms. The case report form is considered as a **source document**. All CRFs will be kept for at least 15 years. The study site will retain a copy of the CRF to ensure that local collaborators can provide access to the source documents to a monitor, auditor, or regulatory agency.

